### **1.3** Study Rationale

Because PAH represents a serious orphan medical condition with a critical need for better therapies, Gossamer Bio, Inc. plans to work closely with the Food and Drug Administration (FDA) in order to ensure an efficient development program.

Gossamer Bio, Inc. will evaluate PK10571 in an initial Phase 1A single-dose/multipledose study in normal, healthy volunteers,

Part A of the phase 1A study is a single ascending dose (SAD) double-blind, placebocontrolled randomized trial of inhaled dry powder PK10571 in healthy human volunteers for determination of safety. Part A will consist of at least 4 cohorts and up to 5 cohorts. Within each cohort, subjects will be randomly assigned to receive either active drug or placebo. The initial dose will be determined based on the results of animal toxicology studies.

After completion and review of the SAD trial (Part A), the multiple ascending dose (MAD) clinical trial (Part B) will be performed. The MAD clinical trial is a doubleblind, placebo-controlled randomized repeat dose trial of inhaled dry powder PK10571 in healthy human volunteers. There will be up to 3 dose cohorts, and within each cohort subjects will be randomly assigned to receive either active drug or placebo. Study subjects will be administered active drug or placebo once daily for 7 days.

Gossamer Bio, Inc.

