### 3.2 Part B

Part B is a multiple ascending dose study design. Subjects will receive either PK10571 or placebo. Approximately 24 subjects will be enrolled in Part B. Subjects will be enrolled in 3 cohorts of 8 subjects each.

Gossamer Bio, Inc.

The initial dose for Part B will be determined after review of the safety and pharmacokinetic data from Part A by the Safety Review Committee.

Data from the lower dose cohort will be analyzed before deciding whether to proceed with the higher dose cohort. Alternatively, a lower dose may be administered, depending upon review of previous cohort's safety and pharmacokinetic data.

Subjects will receive one of the treatments listed in Table 3. The assigned treatment will be given either as a single daily dose (QD), or divided into two daily doses (BID), or divided into three daily doses (TID; each dose to be separated by 6 hours on a given day).

Subjects will be assigned to either active treatment or placebo in randomized fashion.

Table 3Part B: Planned Doses for Cohorts 1–3

| Cohort                 | Test Formulation (n = 6) | Placebo (n = 2) |
|------------------------|--------------------------|-----------------|
| 1                      | PK10571 initial dose     | Placebo         |
| 2                      | PK10571 mid dose*        | Placebo         |
| 3                      | PK10571 high dose*       | Placebo         |
| n = number of subjects |                          |                 |

n = number of subjects

Note: The dosing regimen will be either once daily (QD), twice daily (BID), or three times daily (TID) for 7 consecutive days. For TID dosing, each daily administration will be separated by 6 hours.

\* Alternately, Cohort 2 or 3 will receive a lower dose, depending upon safety and pharmacokinetic data from Cohort 1 or 2, respectively.

Each dose will be administered using an oral inhalation device. Meals will be the same and scheduled at approximately the same times relative to dose for each cohort, if possible. Refer to Section 5.5.1 for details regarding timing of meals for each proposed dosing regimen (QD, BID, and TID).

No water may be consumed for 1 hour prior through 1 hour after each dose, except for 60 mL of room temperature water which will be given to subjects to rinse their mouths after dosing. Subjects will swish the 60 mL of water in their mouths then spit it out.

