Blood samples for pharmacokinetic evaluation will be obtained before the first dose of the day on Day 1 and Day 7 and at selected times through 36 hours after the first dose on Day 1, before the first dose on Days 3-6, through 36 hours after the first dose on Day 7, and on Day 9, Day 10, Day 14, and Day 35.

For QD dosing, a total of 34 pharmacokinetic blood samples will be collected from each subject in Part B.

For BID dosing, a total of 30 pharmacokinetic blood samples will be collected from each subject in Part B.

Gossamer Bio, Inc.

For TID dosing, a total of 30 pharmacokinetic blood samples will be collected from each subject in Part B. Plasma pharmacokinetic samples will be analyzed for PK10571 using a validated analytical method. Appropriate pharmacokinetic parameters will be calculated for each formulation using non-compartmental methods.

Subjects will be housed at the clinical research site for observation until Day 9 (48 hours after the last dose) and return to the clinical research site for safety evaluation and pharmacokinetic blood collection on Days 10, 14, and 35.

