| Dose administration                            |           |              |              | Х       |            |           |           |         |         |         |         |          |          |          |          | Х        |          | Х       | X |   |   |    |    |    |

Gossamer Bio, Inc.

CONFIDENTIAL

| Dent D   |           |              |              |         |            |           |           |         | S       | Study   | Day     | y(s)     |          |          |          |          |          |         |   |   |   |    |    |          |
|--|-----------|--------------|--------------|---------|------------|-----------|-----------|---------|---------|---------|---------|----------|----------|----------|----------|----------|----------|---------|---|---|---|----|----|----------|
| Part B   | -28 to -1 | -1           |              |         |            |           |           |         | 1       |         |         |          |          |          |          | 4        | 2        | 3       | 7 | 8 | 9 | 10 | 14 | 35       |
| Procedure  | Screening | Check-
in | Pre-
dose | 0
hr | 3/5
min | 10
min | 20
min | 1
hr | 2
hr | 4
hr | 8
hr | 10
hr | 12
hr | 16
hr | 20
hr | 24
hr | 36
hr | to
6 |   |   |   |    |    |          |
| Blood collection
for PK analysis j |           |              | Х            |         |            |           |           |         |         | X       |         |          |          |          |          | Х        | Х        | Х       | Х | Х | X | Х  | Х  | X        |
| Urine collection
for PK analysis k |           |              | Х            |         |            |           |           |         |         | Х       |         |          |          |          |          |          |          |         |   |   |   |    |    |          |
| Confinement                          |           | Х            |              |         |            |           |           |         |         |         | Х       |          |          |          |          |          | Х        | Х       | Х | Х | Х |    |    |          |
| Outpatient visits m                   | Х         |              |              |         |            |           |           |         |         |         |         |          |          |          |          |          |          |         |   |   |   | Х  | Х  | X        |

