- h) To be performed on Day 1 predose and 10 minutes postdose (or  $T_{max}$ , based on analysis from previous cohort) and on Day 7 at 10 minutes postdose (or  $T_{max}$ , based on analysis from previous cohort).
- i) To be performed predose on Day 1 and 5 minutes postdose (or Tmax, based on analysis from previous cohort) on Day 1 and Day 7.
- j) Blood samples for pharmacokinetic evaluation will be obtained prior to the first dose administration (predose) on Day 1 and Day 7, and at the following times: Day 1 and Day 7 at 3, 10, 20, 30, and 40 minutes and 1, 2, 4, 8, 12, 24, and 36 hours after dosing; predose on Days 3-6, and on Day 8, Day 9, Day 10, Day 14, and Day 35 (total of 34 samples). For multi-dose administrations, the 3-minute blood collection will be performed after dosing procedures are complete. Exception: For multi-capsule administrations (if required to achieve the dose), the first postdose blood collection will be performed 5 minutes after the start of study treatment administration.
- k) Urine samples for pharmacokinetic analysis will be collected predose (spot collection) and for the first 24 hours after dosing.
- 1) Subjects will remain in the research center for observation until 48 hours after the last dose (Day 9).
- m) Subjects will return to the clinical research site for a safety evaluation and PK blood draws on Days 10, 14, and 35.
- n) Subjects will be monitored for adverse events from the beginning of confinement until the end-of-study visit.
- o) Subjects may undergo a chest x-ray on Day 35 if clinically indicated as determined by the investigator.

Gossamer Bio, Inc.

CONFIDENTIAL

31 Jul 2018

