$\lambda_z (K_{el}, Lambda z)$	Apparent terminal elimination rate constant calculated by linear regression of the terminal linear portion of the log concentration versus time curve, reported to 3 significant figures
T _½	The observed terminal elimination half-life, reported to 3 significant figures and calculated as: $T_{1/2} = \ln(2)/\lambda_z$
CL/F	The apparent total plasma clearance after an inhaled dose, reported to 3 significant figures and calculated as:

Parameter	Definition
	CL/F=Dose/AUC _{0-inf} , where F is the bioavailability
	CL/F will be presented with and without weight-adjustment. Weight adjustment will be calculated as CL/F x 70/body weight in kg.
	The apparent volume of distribution after an inhaled dose, reported to 3 significant figures and calculated as:
V_z/F	$V_z/F=Dose/(AUC_{inf} \times \lambda_z)$, where F is the bioavailability
	Vz/F will be presented with and without weight-adjustment. Weight adjustment will be calculated as Vz/F x 70/body weight in kg.

The following PK parameters will be calculated for PK10571 for multiple ascending dose on Days 1 and 7, unless specified otherwise (MAD, Part B):

Parameter	Definition
C _{max}	Maximum plasma concentration, determined directly from individual concentration-time data, presented to 3 significant figures
	C_{max} will be presented with and without weight-adjustment. Weight adjustment will be calculated as C_{max} x body weight in kg/70.
T_{max}	Time of the maximum plasma concentrations, presented to 3 significant figures
Clast	Last quantifiable plasma concentration determined directly from individual concentration-time data, presented to 3 significant figures
T _{last}	Time of last quantifiable plasma concentration, presented to 3 significant figures
AUC ₀₋₂₄	Area under the plasma concentration-time curve for time zero to 24 hours postdose, presented to 3 significant figures

Parameter	Definition	
	AUC ₀₋₂₄ will be presented with and without weight-adjustment. Weight adjustment will be calculated as AUC ₀₋₂₄ x body weight in kg/70.	
Cavg,ss	Average concentration at steady state, calculated as AUC ₀₋₂₄ /24 h (Day 7 only), presented to 3 significant figures	
CLss/F	Apparent clearance at steady state (Day 7 only), presented to 3 significant figures and calculated as:	
	CLss/F=Total daily dose/AUC ₀₋₂₄ , where F is the bioavailability.	
	CLss/F will be presented with and without weight-adjustment. Weight adjustment will be calculated as CLss/F x 70/body weight in kg.	

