7. SAFETY REVIEW COMMITTEE

The bioanalytical laboratory and pharmacokineticist will be unblinded to allow for analysis and presentation for the assessment by the safety review committee between cohorts. The data presented to the safety review committee will not contain subject-level identifiers in order to maintain the blind of the participants of the safety review unless there is a study emergency. Only the bioanalytical lab and pharmacokineticist will be unblinded for data preparation.

Interim pharmacokinetic analysis will include:

Blinded Concentration vs. Time Table (summary statistics) stratified by Cohort (SAD) and Cohort and Day (MAD)

Mean Concentration vs. Time Profile comparing doses (SAD and MAD) and Days 1 and 7 (MAD)

Mean concentration vs. Time profiles comparing Gender within each Cohort

Blinded PK parameters (summary statistics) stratified by Cohort (SAD) and Cohort and Day (MAD).

Blinded PK parameters (summary statistics) stratified by Cohort and Gender (SAD) and Cohort, Day, and Gender (MAD).

Scatterplots for Part A (SAD):

 $C_{max},\,AUC_{0\text{-}24},\,AUC_{last},\,AUC_{inf},\,and\,\,T_{1/2}$ vs. baseline FVC

 $C_{max},\,AUC_{0\text{-}24},\,AUC_{last},\,AUC_{inf},\,and\,\,T_{1\!\!/_{\! 2}}\,vs.$ baseline FEV1

Scatterplots for Part B (MAD):

C_{max}, AUC₀₋₂₄, and T_{1/2} vs. baseline FVC

C_{max}, AUC₀₋₂₄, and T_{1/2} vs. baseline FEV1

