16.2.6	Individual Efficacy Response Data		
16.2.6.1	PK10571 Plasma Concentration-Time Data Listing by Subject (Part A)		
16.2.6.2	PK10571 Plasma Concentration-Time Data Listing by Subject (Part B)		
16.2.6.3	Plasma Terminal Elimination Rate of PK10571 for Individual Subjects after Single Dose Administrations of FPD (Cohort 1), FPD (Cohort 2), FPD (Cohort 3), FPD (Cohort 4), and FPD (Cohort 5) (Part A)		
16.2.6.4	Plasma Terminal Elimination Rate of PK10571 for Individual Subjects after xx mg FPD (Cohort 1) on Days 1 and 7 (Part B)		
16.2.6.5	Plasma Terminal Elimination Rate of PK10571 for Individual Subjects after xx mg FPD (Cohort 2) on Days 1 and 7 (Part B)		
16.2.6.6	Plasma Terminal Elimination Rate of PK10571 for Individual Subjects after xx mg FPD (Cohort 3) on Days 1 and 7 (Part B)		
16.2.6.7	PK Output text		

Listing Number	Listing Title	Validation Method	Shell Number (if repeat)
16.2.6.8	SAS Output for Part B Day 7 vs Day 1		(======================================
	Comparison (Cohort 1)		
16.2.6.9	SAS Output for Part B Day 7 vs Day 1		
	Comparison (Cohort 2)		
16.2.6.10	SAS Output for Part B Day 7 vs Day 1		
	Comparison (Cohort 3)		
16.2.6.11	SAS Output-Dose Proportionality Assessment		
	Part A		
16.2.6.12	SAS Output-Dose Proportionality Assessment		
	Part B Day 1		
16.2.6.13	SAS Output-Dose Proportionality Assessment		
	Part B Day 7		
16.2.7	Adverse Event Listings		
16.2.7.1	Adverse Event Data – Safety Population	IP	
16.2.8	Individual Laboratory Measurements and		
	Other Safety		
16.2.8.1	Hematology Data – Safety Population	IP	
16.2.8.2	Serum Chemistry Data – Safety Population	IP	
16.2.8.3	Urinalysis Data – Safety Population	IP	
16.2.8.4	Urine Drug, Cotinine and Alcohol Screen –	IP	
30	Safety Population		
16.2.8.5	Serology, PPD and TSH Data – Safety Population	IP	
16.2.8.6	Pregnancy Test and FSH Data – Safety	IP	
	Population		
16.2.8.7	Buffy Coat and Platelet Aggregation Data –	IP	
	Safety Population		
16.2.8.8	Physical Examination Data – Safety Population	IP	
16.2.8.9	Vital Signs Data – Safety Population	IP	
16.2.8.10	ECG Data – Safety Population	IP	
16.2.8.11	Chest X-ray – Safety Population	IP	
16.2.8.12	Prior and Concomitant Medications – Safety	IP	
	Population		
16.2.8.13	Pulmonary Function Data- Safety Population	IP	
16.2.8.14	SAS Mean Difference Output	IP	

Page 39 of 39 Confidential

Signature:

Email: [contact]

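### With once-daily dosing in Part B, the Day 1 36 h PK sample is drawn 12 h after the Day 2 dose, yet the SAP leaves it in the Day 1 summaries, Clast, Tlast and Day 1 versus Day 7 plots

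*Protocol*

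**What the plan says.** **Dosing.** The note to Table 3 in Protocol 3.2 reads "The dosing regimen will be either once daily (QD), twice daily (BID), or three times daily (TID) for 7 consecutive days". In the QD events schedule (Protocol Table 7), the row "Dose administration" is marked at 0 hr, again in the 24 hr column under Day 2, and then on Days 3 to 6 and Day 7.

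**Sampling.** Footnote j to Table 7 gives one list of times for both Day 1 and Day 7, from 3 minutes "and 40 minutes and 1, 2, 4, 8, 12, 24, and 36 hours after dosing; predose on Days 3-6". Protocol 3.2 likewise describes sampling "at selected times through 36 hours after the first dose on Day 1". Protocol Appendix 1 and SAP 6.2.10 repeat the schedule.

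**Analysis.** SAP 6.2.11 opens its Part B table with "The following PK parameters will be calculated for PK10571 for multiple ascending dose on Days 1 and 7, unless specified otherwise". Average steady-state concentration, CLss/F, Vz/F, lambda-z and half-life are then marked as Day 7 only. Clast and Tlast carry no such mark. They are defined as the final quantifiable level and its time, with no cut at 24 h or at the next dose. Concentrations are summarised by day at each nominal time. SAP 6.2.10 plans Day 1 versus Day 7 plots, both as cohort means and by subject, and 36.00 h is among its nominal times. Listings 16.2.6.4 to 16.2.6.6 in SAP Appendix 1 name a terminal elimination rate for both days.

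**The concern.** The label 36 h means two different things. On Day 7 it is 36 h after the last dose. On Day 1 it follows a second dose. Nothing in either document ends the Day 1 profile before Dose 2 or flags the 36 h value. Followed literally, the plan would report a level that comes mostly from Dose 2 as first-dose exposure, and would give a Day 1 Tlast of about 36 h that belongs to a different dose. The late end of the Day 1 versus Day 7 plot would also compare unlike times since dosing.

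**Working it through.** **1. Is the Day 1 36 h sample a separate, intended draw?** The protocol states 34 samples for QD. From footnote j:

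- predose on Days 1 and 7: 2
- 12 postdose times on each of the two days: 2 × 12 = 24
- predose on Days 3 to 6: 4
- Days 8, 9, 10, 14 and 35: 5

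The sum is 35. The Day 8 sample and the 24 h sample after the Day 7 dose are the same draw, so the count is 35 − 1 = 34. This matches the stated figure, with the Day 1 36 h sample counted as its own draw. Table 7 also marks PK blood in the 36 hr column.

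**2. Time since last dose.** QD doses fall at 0, 24, 48, 72, 96, 120 and 144 h.

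- Day 1 36 h sample: 36 − 24 = 12 h after Dose 2.
- Day 7 36 h sample: (144 + 36) − 144 = 36 h after Dose 7.

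The Day 1 24 h sample is clean. Protocol 5.7 allows only an early window of 5 minutes when a later draw coincides with a dose. In the BID and TID schedules the last Day 1 draw is at 24 h (12 h after the second or third dose respectively), so neither series runs past the first Day 2 dose.

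**3. Size.** The documents give no half-life h, so it is assumed over a range. The model is mono-exponential with equal doses and superposition, C(t) = 2^(−t/h), and r = 2^(−24/h).

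- Share of the Day 1 36 h level from Dose 2 = C(12)/[C(12) + C(36)] = 1/(1 + r)
- Inflation over a true first-dose 36 h level = 1 + 1/r
- True ratio, Day 7 to first dose, at 36 h = 1 + r + … + r^6
- Plotted Day 1/Day 7 ratio = (1 + 1/r)/(1 + r + … + r^6)

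Worked case, h = 12: r = 0.25. The share is 1/1.25 = 80%, the inflation is 1 + 4 = 5, the true ratio is 1.33, and the plotted Day 1/Day 7 ratio is 5/1.33 = 3.75.

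| Assumed half-life (h) | Dose 2 share | Inflation | True Day 7/first-dose ratio | Plotted Day 1/Day 7 ratio |
|---|---|---|---|---|
| 4 | 98.5% | 65 | 1.02 | 64 |
| 8 | 88.9% | 9 | 1.14 | 7.9 |
| 12 | 80.0% | 5 | 1.33 | 3.75 |
| 24 | 66.7% | 3 | 1.98 | 1.5 |
| 36 | 61.4% | 2.6 | 2.60 | 0.997 |
| 48 | 58.6% | 2.4 | 3.11 | 0.78 |

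The share exceeds one half at every half-life, because r is below 1. The plotted Day 1 point lies above Day 7 only for half-lives below about 36 h.

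**4. Which outputs use the sample?**

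- *Affected:* Day 1 concentration summaries and profiles; the Day 1 versus Day 7 figures (14.4.7 to 14.4.9 and 14.4.13 to 14.4.15); Day 1 Clast and Tlast where the 36 h value is quantifiable. SAP 6.2.11 treats a trailing BLQ value as missing, so a BLQ result leaves Clast and Tlast unchanged.
- *Not affected:* AUC0-24, the accumulation ratio Rac, the Day 7 versus Day 1 ANOVA and the dose-proportionality model on AUC0-24, and the regression of Day 3 to 7 troughs.
- *Unlikely to change:* Cmax, since the extra sample is 12 h after a dose.

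**5. The listings.** SAP 6.2.11 limits lambda-z to Day 7, while three listing titles ask for Day 1 as well. If a Day 1 rate were fitted through 12, 24 and 36 h, the least-squares slope under the same model would be ln(1 + r)/24. This is positive at every half-life (+0.0006 per h at h = 4, +0.017 at h = 24), so those points yield no half-life.

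**The case against.** The strongest reply is that little depends on this sample. Day 1 Clast and Tlast feed no other Part B parameter in the SAP, since the Part B list has neither AUClast nor AUCinf. The formal comparisons use Cmax and AUC0-24. QD is one of three possible regimens, and an experienced pharmacokineticist might end the profile at 24 h unprompted. The listing titles are declared open to change. All of this stands, and it sets the severity. It does not remove the defect, because the written rule still gives the wrong Day 1 value and the SAP does not say to truncate.

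Three stronger readings are tempting, and the documents do not support them.

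- *The Safety Review Committee would be misled about accumulation.* SAP section 7 puts a Day 1 and Day 7 mean profile in the committee's package, but no text says the committee judges accumulation from it. Protocol 3.4 names Cmax and AUC as the PK factors for escalation. The package also includes PK parameters by cohort and day, among which AUC0-24 and Rac are sound.
- *The plot always points the wrong way.* It does so only below a half-life of about 36 h. The largest distortions also occur where accumulation is slight: at 4 h the true ratio is 1.02.
- *Every active QD subject has a wrong Clast and Tlast.* This holds only for quantifiable 36 h values, and the documents give no quantitation limit from which to predict how many.

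**Conclusion.** The point holds for QD cohorts, as a minor one. The timing follows directly from the dosing and sampling schedules and needs no model. As the SAP stands, a level 12 h after Dose 2 is reported under Day 1 at 36 h, and it becomes Day 1 Clast and Tlast whenever it is quantifiable. The size rests on assumed mono-exponential decline, equal doses and an unknown half-life: the Dose 2 share runs from 98.5% at 4 h to 58.6% at 48 h. The effect is confined to descriptive outputs. The mismatch between Listings 16.2.6.4 to 16.2.6.6 and the Day 7 only rule for lambda-z is a small related inconsistency, not evidence that a Day 1 half-life is planned.

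**What to change.** 1. State in SAP 6.2.10 and 6.2.11 that the QD Day 1 profile ends at the 24 h sample drawn before Dose 2.
2. Label the 36 h draw as 12 h after Dose 2. List it under that label, and leave it out of Day 1 Clast, Tlast, concentration summaries and all Day 1 versus Day 7 figures.
3. Restrict the titles of Listings 16.2.6.4 to 16.2.6.6 to Day 7, in line with SAP 6.2.11.

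The cost is SAP wording and output labels. The draw need not be dropped: it is a valid 12 h level after Dose 2, and keeping it leaves the count at 34 samples and 204 mL. AUC0-24 and Rac are the same before and after the change.

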## APPENDIX 1 PHARMACOKINETIC BLOOD SAMPLE COLLECTION, PROCESSING, AND SHIPMENT INSTRUCTIONS

## A. Collection and Processing

A more detailed description of plasma sample preparation requirements may be provided by the analytical laboratory. If such a description is provided, the method of sample preparation provided by the laboratory shall supersede those provided in this protocol and appropriate documentation shall be placed in the investigator site file.

|    | Processing Instructions   |
|----|---|
| 1  | Blood samples will be collected into 6 mL Vacutainer tube(s) containing K 2 -EDTA.
The time and date of collection for each sample will be recorded. Samples will be
placed on ice after collection and remain on ice throughout processing.   |
|    | PART A: Samples will be collected at 0 hour (predose) and then at 3, 10, 20, 30, 40 minutes, and 1, 2, 4, 8, 12, 24, 36, and 48 hours after study treatment administration.  |
| 2A | (Note: The predose sample will be collected within 150 minutes of dose
administration. Predose blood samples obtained from backup subjects who are
randomized into the study may exceed the predose collection window.)   |
|    | PART B: If QD dosing: Blood samples for pharmacokinetic evaluation will be
obtained prior to the first dose administration (predose) on Day 1 and Day 7, and at
the following times: Day 1 and Day 7 at 3, 10, 20, 30, and 40 minutes and 1, 2, 4, 8,
12, 24, and 36 hours after dosing; predose on Days 3-6, and on Day 8, Day 9, Day 10,
Day 14, and Day 35 (total 34 samples).   |
| 2B | If BID dosing: Blood samples for pharmacokinetic evaluation will be obtained prior
to the first dose administration (predose) on Day 1 and Day 7 and at the following
times after each dose (2 per day) on Day 1 and Day 7: 3 and 30 minutes and 2, 8, and
12 hours. Blood samples will also be collected before the first dose on Days 3-6, and
on Day 8, Day 9, Day 10, Day 14, and Day 35 (total of 30 samples).   |
|    | If TID dosing: Blood samples for pharmacokinetic evaluation will be obtained prior
to the first dose administration (predose) on Day 1 and Day 7, and at the following
times after each dose (3 per day) on Day 1 and Day 7: 3 and 40 minutes and 6 hours.
An additional sample will be obtained on Day 2 (12 hours after the 3 rd dose on
Day 1). Blood samples will also be collected before the first dose on Days 2-6, and on
Day 8 (6 hours and 12 hours after the 3 rd dose on Day 7), Day 9, Day 10, Day 14, and
Day 35 (total of 30 samples). For multi-capsule administrations (if required to
achieve the dose), the first postdose blood collection will be performed 5 minutes
after the start of study treatment administration. |

| 3 | The predose sample on Day 1 will be collected within 150 minutes of dose
administration. Predose blood samples obtained from backup subjects who are
randomized into the study may exceed the predose collection window. |
|---|--|
| 4 | Blood samples will be centrifuged at approximately 3000 rpm for 10 minutes at 4 degrees Centigrade.  |
| 5 | The resulting plasma samples will be harvested and transferred in approximately equal aliquots into two appropriately labeled polypropylene screw-cap tubes.   |
| 6 | Samples will be placed in an upright position in a freezer at approximately -20 degrees Centigrade within 60 minutes of collection.  |
| 6 | Samples will remain frozen until assayed.  |

|                          |  | Part                 | A Sample Collect | ion Summary                            |                            |
|--------------------------|--|----------------------|------------------|--|----------------------------|
| Number
of
Subjects | Number of
time points
per period | Number
of Periods | Sample type      | Tube type                              | Number of tubes per sample |
| Up to 40                 | 14                                     | 1                    | Collection       | 6 mL K 2 EDTA
Vacutainer | 1                          |
|                          | * I                                    | 1                    | Aliquot          | 3 mL Polypropylene
screw Cap        | 2                          |

|                          |  | Part                 | B Sample Collect | ion Summary                            |                            |
|--------------------------|--|----------------------|------------------|--|----------------------------|
| Number
of
Subjects | Number of
time points
per period | Number
of Periods | Sample type      | Tube type                              | Number of tubes per sample |
| Up to 24                 | 34 (if QD)
30 (if BID)              | 1                    | Collection       | 6 mL K 2 EDTA
Vacutainer | 1                          |
| 00021                    | 30 (if TID)                            | Ĩ                    | Aliquot          | 3 mL Polypropylene
screw Cap        | 2                          |

